2.2 RISKS ANALYSIS AND RISK ASSESSMENT

2.2.1 POTENTIAL ANTICIPATED ADVERSE EVENTS

An adverse event is any clinical event that impacts, or that has the potential to impact, the health or safety of a Clinical Study subject caused by or associated with the study device and/or testing. Assessment for potential adverse events will be ongoing throughout this trial.

The benefits of treatment may include improvement in the frequency, or severity of urine loss, and improvement in quality of life. Decreases in serum triglycerides, cholesterol, and body fat, and improvements in insulin resistance, lean body mass and physical endurance are also possible benefits.

Adverse event tables and serious adverse events discussed below and are presented separately by adverse events reported among healthy volunteers on a single trial of 86 days of GTx-024 3 mg versus placebo and those enrolled on cancer trials of at least 86 days exposure to GTx-024 3 mg or placebo.

Adverse events reported among > 5% of GTx-024 3mg treated healthy subjects
Percentage of subjects reporting a given adverse event at least once

Primary System Organ Class	Preferred Term	GTx-024 N=24	Placebo N=24
Gastrointestinal disorders	Diarrhea	8.3	12.5
	Dyspepsia	8.3	8.3
	Vomiting	8.3	0.0
General disorders and administration site conditions	Vessel puncture site bruise	12.5	4.2
	Fatigue	8.3	8.3
	Malaise	8.3	0.0
Infections and infestations	Herpes simplex	8.3	0.0
Injury, poisoning and procedural complications	Contusion	8.3	4.2
Investigations	Alanine aminotransferase increased	20.8	0.0
Musculoskeletal and connective tissue disorders	Back pain	12.5	16.7

Primary System Organ Class	Preferred Term	GTx-024 N=24	Placebo N=24
Nervous system disorders	Headache	20.8	20.8
	Dizziness	12.5	4.2
Respiratory, thoracic and mediastinal disorders	Pharyngolaryngeal pain	12.5	12.5

No serious adverse events (SAEs) were reported on this trial.

These side effects are based on information obtained from a clinical study (G200501) administering GTx- 024 3 mg for 86 days in healthy subjects– elderly males and postmenopausal females. Studies suggest that side effects associated with the study drug resolve after GTx-024 is stopped.

**Adverse events reported among > 5% of GTx-024 3 mg treated cancer subjects
Percentage of subjects reporting a given adverse event at least once**

Primary System Organ Class	Preferred Term	GTx-024 N=432	Placebo N=378
Blood and lymphatic system disorders	Anemia	34.7	34.7
	Neutropenia	18.3	23.3
	Thrombocytopenia	10.4	10.8
	Leukopenia	8.3	9.0
Gastrointestinal disorders	Nausea	34.7	34.9
	Vomiting	20.1	21.2
	Constipation	12.3	10.1
	Diarrhea	11.6	12.7
General disorders and administration site conditions	Abdominal pain	5.1	3.7
	Fatigue	15.7	16.7
	Asthenia	15.3	13.5
	Disease progression	11.8	16.7
Infections and infestations	Pyrexia	10.2	9.8
	Pneumonia	5.6	7.1
Investigations	Blood creatinine increased	8.1	5.0

Primary System Organ Class	Preferred Term	GTx-024 N=432	Placebo N=378
	Weight decreased	6.0	4.8
Metabolism and nutrition disorders	Decreased appetite	10.6	14.8
Musculoskeletal and connective tissue disorders	Arthralgia	8.1	7.9
	Pain in extremity	5.6	4.2
Nervous system disorders	Headache	7.4	6.1
	Peripheral sensory neuropathy	5.8	3.4
	Dizziness	5.6	6.3
Respiratory, thoracic and mediastinal disorders	Dyspnoea	12.3	7.4
	Cough	9.5	9.3
Skin and subcutaneous tissue disorders	Alopecia	17.8	18.5

Serious adverse events (SAEs) reported among > 2% of GTx-024 3 mg treated cancer subjects

Percentage of subjects reporting a given serious adverse event at least once

Primary System Organ Class	Preferred Term	GTx-024 N=432	Placebo N=378
Blood and lymphatic system disorders	Anemia	4.2	3.7
	Neutropenia	3.2	3.7
	Febrile neutropenia	2.3	1.6
Blood and lymphatic system disorders	Thrombocytopenia	2.3	1.6
General disorders and administration site conditions	Disease progression	7.9	11.9
Infections and infestations	Pneumonia	3.5	3.2
Neoplasms benign, malignant and unspecified (incl cysts and	Malignant neoplasm progression	2.8	2.1

An AE that appears related to GTx-024 in clinical trials has been a dose-dependent, transient, asymptomatic increase in ALT. However, these increases were modest at doses up to 10 mg per day. Most of the subjects studied to date had ALT levels that

remained within normal limits. One subject was discontinued for an ALT > 3 times the ULN. The ALT levels returned to normal with continued exposure to GTx-024 in most cases and, further, in instances when dosing was not continued, levels returned to normal. No significant increases in total bilirubin, gamma glutamyl transferase, alkaline phosphatase, or lactate dehydrogenase have been observed in subjects with elevated ALT levels. Consistent with the effects of other orally administered anabolic agents, GTx-024 causes a dose dependent reduction in high-density lipoprotein (HDL), the clinical significance of which is unknown at this time. The proposed mechanism for reduction in HDL is due to stimulation of reverse cholesterol transport and increased HDL catabolism by hepatic lipase. Reductions in HDL are temporary and typically return to baseline 12 months after treatment initiation.

The effect of GTx-024 on a fetus has not been evaluated; therefore, the subjects in the current investigation will be post-menopausal.

2.2.2 STUDY RISKS

Study Procedures

Urethral catheterization

Less Frequent (occurring more than 1%, but less than 10% of the time)

Discomfort

Mild cramping

Infection

Rare (occurring less than 1% of the time)

Bleeding

Urinary tract infection

Inability to pass urine

Puncture of the bladder

Burning with urination

Antibiotic (a medicine to prevent infection)

Less Frequent (occurring more than 1% but less than 10% of the time)

Diarrhea

Nausea and vomiting

Cramping

Rare (occurring less than 1% of the time)

Headache

Itching

Rash

Allergic reaction

Blood Drawing

Most Frequent (occurring more than 10% of the time):

Pain

Bleeding

Bruising at the needle puncture site
Rare (occurring less than 1% of the time):
Blood clot
Infection
Feeling lightheaded
Fainting

Mammogram

Most Frequent (occurring more than 10% of the time):
Discomfort

Gynecological Exam

Rare (occurring less than 1% of the time):
Discomfort

Pelvic MRI

Rare (occurring less than 1% of the time):
Discomfort

2.2.3 METHODS TO MINIMIZE RISK

Subjects will be monitored at each visit for changes since last visit and adverse effects of treatment. Since elevations in ALT are possible, serum liver function tests will be monitored during treatment. (Refer to Section 9.4 Halting Rules)

Subjects will receive a prophylactic antibiotic at visits where catheterization/UPP occur to decrease risk of urinary tract infection (UTI). Any infection will be appropriately treated.

3. OBJECTIVES

3.1 PRIMARY OBJECTIVE

1. Describe the effect of 12 weeks of treatment of GTx-024 on the number of stress incontinence episodes/day as assessed by the 3 day voiding diary.

3.2 SECONDARY OBJECTIVES

1. Describe the effect of 12 weeks of treatment of GTx-024 on the frequency of voids/day as assessed by the 3 day voiding diary.
2. Describe the effect of 12 weeks of treatment of GTx-024 on urine volume per void as assessed by the 3 day voiding diary.

3. Describe the effect of 12 weeks of treatment of GTx-024 on SUI as assessed by 24 hour pad weight test.
4. Describe the effect of 12 weeks of treatment of GTx-024 on SUI as assessed by the Urethral Pressure Profile (UPP).
5. Describe the effect of 12 weeks of treatment of GTx-024 on SUI as assessed by the Bladder Stress Test.
6. Describe the effect of 12 weeks of treatment of GTx-024 on patient reported stress urinary incontinence symptoms as assessed by the MESA Urinary Questionnaire.
7. Describe the effect of 12 weeks of treatment of GTx-024 on patient reported impression of symptom severity as assessed by the Patient Global Impression of Severity Scale (PGI-S).
8. Describe the effect of 12 weeks of treatment of GTx-024 on patient reported impression of improvement as assessed by the Patient Global Impression of Improvement Scale (PGI-I).
9. Describe the effect of 12 weeks of treatment of GTx-024 on patient reported urogenital distress as assessed by the Urinary Distress Inventory Questionnaire (UDI-6).
10. Describe the effect of 12 weeks of treatment of GTx-024 on patient reported impact of urinary incontinence on daily life as assessed by the Incontinence Impact Questionnaire (IIQ-7).
11. Describe the effect of 12 weeks of treatment of GTx-024 on patient reported sexual function as assessed by the Female Sexual Function Index Questionnaire (FSFI).
12. Describe the effect of 12 weeks of treatment of GTx-024 on pelvic floor muscles as measured by MRI.

3.3 STUDY END POINTS

Primary end point

1. Change in frequency of daily stress urinary incontinence episodes from Baseline to Week 12.

Secondary end points

1. Change in frequency of daily voids from Baseline to Week 12.
2. Change in urine volume per void from Baseline to Week 12.
3. Change in 24 hour pad weight from Baseline to Week 12.
4. Change in maximum urethral closure pressure measurements from Baseline to Week 12.
5. Change in urine leakage (yes/no) on the Bladder Stress Test from Baseline to Week 12 as assessed while (a) coughing, and/or (b) performing a Valsalva maneuver.
6. Change in total score on the stress incontinence section of the MESA Urinary Questionnaire from Baseline to Week 12.
7. Change in Patient Global Impression of Severity (PGI-S) Scale from Baseline to Week 12.
8. Patient Global Impression of Improvement (PGI-I) Scale at Week 12.
9. Change in total score on the Urinary Distress Inventory (UDI-6) from Baseline to Week 12.
10. Change in total score on the Incontinence Impact Questionnaire (IIQ-7) from Baseline to Week 12.
11. Change in total score on the Female Sexual Function Index (FSFI) from Baseline to Week 12 as well as the change in subdomain scores: libido, arousal, lubrication, orgasm, satisfaction, and pain.
12. Change in pelvic floor muscles from Baseline to Week 12 as measured by MRI. Quantitative assessments may include the area of the levator hiatus, the anteroposterior and transverse diameters, and other relevant parameters.

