5. STUDY ENROLLMENT AND WITHDRAWAL

5.1 SUBJECT INCLUSION CRITERIA

Subject Inclusion Criteria: Subjects eligible for inclusion in this study must meet **all** of the following criteria:

1. Give voluntary, written and signed, informed consent
2. Female
3. Age 18 to 80 years old
4. Clinically confirmed as postmenopausal. Subjects must have undergone the onset of spontaneous, medically induced or surgical menopause prior to the start of this study. Postmenopausal is defined as 12 months of spontaneous amenorrhea or 6 months of spontaneous amenorrhea with serum FSH levels > 40 mIU/ml or 6 weeks postsurgical bilateral oophorectomy with or without hysterectomy.
5. SUI symptoms for at least 6 months duration
6. Predominant SUI (MESA questionnaire)
7. 24 hour pad weight >3 gms at baseline
8. At least 4, but no more than 15, SUI episodes on each day of the 3 day baseline voiding diary.
9. Serum AST and ALT within normal limits
10. Total bilirubin within normal limits
11. Positive Bladder Stress Test
12. Subject agrees to not start any new treatment (medication or otherwise) that is known to affect lower urinary tract function throughout the treatment and follow up periods.
13. Subject agrees to maintain on a stable dose of any medication known to affect lower urinary tract function, including but not limited to anticholinergics, tricyclic antidepressants, or alpha-adrenergic blockers, throughout the treatment and follow-up period.

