7. STUDY SCHEDULE

7.1 STUDY VISITS

Each subject may complete up to 5 months of study participation.

Screening Visit, Days -21-0

The study will be explained in detail and adequate time will be allowed for answering potential subjects questions prior to signing the IRB approved informed consent document. Informed consent will be obtained from those volunteers meeting initial inclusion/exclusion criteria and expressing willingness to participate prior to conducting any further study tests or measures.

Once informed consent is obtained, a detailed interview with vital signs will be conducted to further review for inclusion/exclusion criteria. A subject number will be assigned. Height and weight will be measured. Subjects will complete the MESA questionnaire to assess incontinence type (stress, urge, or mixed). If urinary incontinence type is stress predominant, then the subject will be instructed to complete a 24 hour pad weight and 3 day voiding diary prior to the next study visit. A bladder

stress test will be done to confirm SUI. Lab tests will also be drawn at this visit as outlined in Table I. A baseline urinalysis will be obtained. Concomitant medications will also be assessed and recorded.

Additional Screening, Days -21-0

If the subject has qualified for the study during the Screening visit, the following procedures will be performed between Screening Visit and Visit 1. Mammogram, if not done within the last 6 months, will be performed. Pelvic MRI will be performed

Study Visit 1: Week 0, Clinic Visit

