8. STUDY PROCEDURES/EVALUATIONS

Please see Table 1 Schedule of Measures for an outline of the timing of the study procedures. Please see Appendix A, B, C, D, E for outcomes measures.

Interview with Vital Signs

All potential subjects will be interviewed/assessed to confirm inclusion/absence of exclusion criteria. A review of systems will be completed, concomitant medications will be assessed, and vital signs (temperature, blood pressure, pulse and respirations) will be assessed. Laboratory results will also be reviewed at specified time points as outlined in Table 1.

History

A detailed history will include review of gravida, prior abortions, parity, deliveries, and history of gynecological conditions and/or cancer.

Focused Physical Exam

A standard brief physical exam will be done. This will include a gynecological pelvic exam and visual skin exam with specific attention to androgenic changes.

Urinalysis

A clean catch midstream voided urine specimen will be obtained, and evaluated by urine dipstick. If results or clinical symptoms indicate, the specimen will be sent for culture and the patient will receive appropriate treatment for UTI per standard of care.

24 Hour Pad Weight Test

The 24-hour pad test should be completed during 1 day of each scheduled 3-day diary. Subjects will be instructed to record pad weight on a day that is typical for them in terms of activity level and fluid intake. Subjects should be given one type of incontinence pad at the clinic. They may choose from a "light" pad or a "heavy" pad, but the pads dispensed **MUST** be used for the 24-hour test. Subjects should receive 8 incontinence pads for use during each 24-hour test period.

Urethral Pressure Profile (UPP) and Bladder Stress Test

To conduct the UPP and Bladder Stress Test, a urodynamic catheter will be placed and the bladder will be filled with 300 ml of fluid, such as saline. UPP will be performed. Subjects will be instructed to perform a provocative maneuver to increase abdominal pressure (cough, Valsalva, or similar event). Urine loss during this event indicates a positive stress test.

Ultrasound Bladder Scan

Subjects will be asked to void, and the volume of urine remaining in the bladder after voiding (post void residual) will be measured via bladder ultrasound scan.

Mammogram

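### The Bladder Stress Test endpoint uses as Baseline the Screening test that must be positive for entry, so its overall yes/no result can only improve; section 10.1 gives it no analysis

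*Combined protocol and SAP*

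**What the plan says.** Section 3.3 lists as secondary endpoint 5 "Change in urine leakage (yes/no) on the Bladder Stress Test from Baseline to Week 12", assessed on coughing, Valsalva or both. Inclusion criterion 11 in section 5.1 is "Positive Bladder Stress Test". Section 8 defines positivity by the same event that the endpoint counts: "Urine loss during this event indicates a positive stress test".

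Section 7.1 places the pre-treatment test at the Screening visit, where a bladder "stress test will be done to confirm SUI". Table 1 marks the test at Screening and Week 12 only, and the Visit 1 text in section 7.1 does not mention it. Section 8, however, describes the stress test and the UPP together, and says that for them "a urodynamic catheter will be placed and the bladder will be filled with 300 ml of fluid". Table 1 has the UPP at Visit 1 and Week 12.

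Endpoint 6 is "Change in total score on the stress incontinence section of the MESA Urinary Questionnaire from Baseline to Week 12". MESA is also completed at Screening, where it decides incontinence type for inclusion criterion 6, and it is not among the Visit 1 questionnaires. Criterion 6 asks for stress predominance and sets no cut-off on the stress score.

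Section 10.1 gives an analysis for eleven of the twelve secondary endpoints. The one without is endpoint 5, which is also missing from the secondary measures listed in section 10.

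**The concern.** A result that admits a subject should not also be the starting point for measuring her change. Some women who leak at Screening would not leak on a second test a few weeks later, treated or not. If the first test must be positive, those women appear only as improvements. The opposite cases, negative first and positive later, were excluded at entry and cannot offset them. A concurrent control arm would show how large this effect is, but the study is single-arm and open-label.

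What is at stake is how one secondary result is read. Section 10.1 looks ahead to estimating effect size and sample size for later trials if the compound shows promise. A conversion rate that is partly retest variation could be carried into that planning as drug effect. Without a planned analysis, nothing would tell the reader that Baseline was fixed at 100% positive.

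**Working it through.** **1. Which value is Baseline?** From Table 1:

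| Measure | Screening | Visit 1 | Week 4 | Week 8 | Week 12 |
|---|---|---|---|---|---|
| Bladder Stress Test | yes | no | no | no | yes |
| UPP | no | yes | no | no | yes |
| MESA | yes | no | yes | yes | yes |
| UDI-6, IIQ, PGI-S, FSFI | no | yes | yes | yes | yes |

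For the stress test and MESA, the only scheduled pre-dose value is the Screening one.

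**2. Possible changes.** Code leakage as 1 and no leakage as 0. Criterion 11 sets the overall Baseline to 1 for everyone, so change = Week 12 result − 1, which is 0 or −1. This step needs no assumed figure.

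**3. Size with no drug effect.** The plan gives no figure for this endpoint to reproduce. The number of completers, n = 30, is from section 10. The probability p that an untreated repeat is positive is not in the documents, so a range is assumed. Expected conversions = n(1 − p):

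- p = 0.95: 30 × 0.05 = 1.5
- p = 0.90: 30 × 0.10 = 3
- p = 0.80: 30 × 0.20 = 6

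If 35 are recruited and 20% withdraw (the upper figure in section 10), 35 × 0.80 = 28 complete, and the values become 1.4, 2.8 and 5.6.

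**4. The same case with an ungated Visit 1 Baseline.** Among women positive at Screening, let q = 1 − p be the chance of a negative at Visit 1 and, with no drug effect, at Week 12. Assuming the two tests are independent, expected conversions in each direction = nq(1 − q):

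- q = 0.05: 30 × 0.05 × 0.95 = 1.4
- q = 0.10: 30 × 0.10 × 0.90 = 2.7
- q = 0.20: 30 × 0.20 × 0.80 = 4.8

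Improvements and worsenings balance, so the expected net change is zero.

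**5. MESA.** Selection was simulated as stress index above urge index at Screening. Assumed inputs, none given in the documents for the stress score: SD 18 percentage points, stress–urge correlation 0.3, retest correlation 0.70 to 0.89, and means of 60 for stress and 40 or 60 for urge. The spurious mean fall is 0.14 to 0.93 of 27 points, and 40% to 48% of subjects still score worse on retest. The bias favours benefit, but it is small and two-way.

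**The case against.** The strongest reply is that the study sets out to describe. It claims no power, and this is one binary endpoint among twelve secondary ones. The proportion negative at Week 12 among women positive at Screening is a legitimate descriptive result. That stands: neither the primary endpoint nor the sample size is affected. It still leaves the endpoint defined as a change from a Baseline that cannot vary, with no analysis given.

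Section 8 can also be read as making the provocative manoeuvre part of every UPP, in which case it may already be done at Visit 1. That doubt stands too. Table 1 and the Visit 1 text do not schedule it, so the passages need reconciling. The pairing raises a further question: Table 1 shows no UPP at Screening, so it is unclear whether the Screening test is done under the same filling conditions as Week 12.

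Four stronger readings are tempting, and the documents do not support them.

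- A reader might infer a false claim of significance. Six one-way conversions would give an exact two-sided McNemar p of 2 × 0.5^6 = 0.031, and the chance of at least six of 30 is 0.3%, 7% or 57% at the three assumed rates. The plan names neither that test nor a significance level for this endpoint, and those rates are not in the documents.
- A reader might infer that no worsening of any kind can be recorded. The endpoint covers cough and Valsalva, so a woman positive on cough alone at Screening could newly leak on Valsalva at Week 12. The one-way argument holds for the overall result only.
- A reader might infer that MESA has the same defect. Entry is on incontinence type while the endpoint is the stress score, so its bias is ordinary regression to the mean.
- A reader might infer that a Visit 1 Baseline would isolate the drug effect. It would not remove placebo response: section 2.1 itself cites placebo-group falls in episode frequency of 27% and 41% in duloxetine studies.

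**Conclusion.** The point holds for the overall yes/no stress-test result. Its structure follows from criterion 11, the Table 1 timing and the single-arm design, without any assumed number. Its size does rest on an assumption: with 30 completers, 1.5 to 6 spurious conversions (5% to 20%) for repeat-positive probabilities of 0.95 down to 0.80. If the test is highly repeatable, the bias is small. The missing analysis in section 10.1 is a plain omission whatever the retest rate. The MESA effect is a minor note. The change is worth making because it is cheap, although it concerns the interpretation of one secondary endpoint only.

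**What to change.** - State that inclusion criteria 6 and 11 are judged on Screening results only. Table 1 rechecks eligibility at Visit 1, so without this sentence a negative repeat would conflict with entry.
- At Visit 1, before the first dose and while the bladder is filled for the UPP, record the cough and Valsalva results by manoeuvre and overall. Use these as Baseline without gating entry.
- Reconcile section 8 with Table 1 on when the stress test is done and whether it accompanies the catheterised UPP, so that the Baseline and Week 12 tests are done under the same conditions.
- Add MESA to the Visit 1 questionnaires and use that score as its Baseline.
- Add endpoint 5 to section 10.1: the proportion negative at Visit 1 and at Week 12, each with an exact 95% confidence interval, and the paired change.
- If no repeat is added, report the proportion negative at Week 12 with an exact confidence interval and state that Baseline was 100% positive by design.

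The cost is one extra manoeuvre within a procedure already scheduled, one short form at an existing visit, and a clarifying sentence on eligibility.

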4. METHODOLOGY

4.1 STUDY DESIGN

This is a single site, proof of concept feasibility study to describe the effect of GTx-024 3 mg in postmenopausal female subjects with SUI. Postmenopausal will be defined as clinically confirmed female subjects who have undergone the onset of spontaneous, medical or surgical menopause prior to the start of this study. Durability of treatment will also be explored by evaluating validated measures at 4 weeks after last dose. Up to 35 subjects will be enrolled in this study.

Institutional Review Board (IRB) approval from Beaumont's Human Investigations Committee will be obtained prior to beginning any study activity. Once IRB approval is obtained, potential participants will be identified from existing medical records, or physician or other referrals.

Potential subjects may be prescreened by telephone prior to the first in person study visit (initial screening visit). At the first in person study visit, subjects will be seen in the Urology Clinical Research space and informed consent will be obtained prior to any study activity. At Study Visit, 2, inclusion/exclusion criteria will be verified, study data will be collected, and consented participants may begin treatment.

Enrolled subjects will agree to maintain on a stable dose of any medication known to affect lower urinary tract function, including but not limited to anticholinergics, tricyclic antidepressants, or alpha-adrenergic blockers, throughout the treatment and follow-up period. Subjects enrolled in the study will agree to not start any new treatment (medication or otherwise) that is known to affect lower urinary tract function throughout the treatment and follow up periods. Subjects will also agree to refrain from performing any Kegal exercises and maintain current dietary habits throughout the treatment and follow up periods.

